#### Non-hematological Toxicity:

- Any Grade 3 or greater, non-hematological toxicity will be considered a DLT with the following *exceptions*:
  - a. Pain and sensory neuropathy are expected toxicities of dinutuximab, but pain or sensory neuropathy at levels described in Table 8: Adverse Reactions Requiring Permanent Discontinuation of Dinutuximab will be considered a DLT. Pain requiring sedation and respiratory support for control will also be considered a DLT.
  - b. Tumor lysis syndrome, including associated abnormalities (e.g., electrolytes, uric acid, renal function).
  - c. Grade 3 low electrolyte levels that are correctable and asymptomatic.
  - d. Grade 3 hypoalbuminemia. Such individuals should receive supplementation as indicated. Hypocalcemia toxicity grade should be assigned based on the calcium level corrected for degree of hypoalbuminemia according to the following formula: for every albumin decrease of 1 gm/dL a total calcium increase of 0.2 mmol/L is to be made.
  - e. Grade 3 transaminase, alkaline phosphatase, bilirubin or other liver function test elevation, provided there is resolution to  $\leq$  grade 2 with supportive care within 7 days and is not associated with other clinically

significant consequences. Grade 3 transaminase elevation, alkaline phosphatase or hyperbilirubinemia elevation of any duration in patients with liver involvement due to tumor will not be considered a DLT, although Grade 4 hepatic toxicity will be considered DLT.

- f. Transient Grade 3 nausea, vomiting, diarrhea, local reactions, influenza-like symptoms, myalgias, fever, headache, acute pain, or skin toxicity that resolves to ≤Grade 2 within ≤72 hours after medical management (e.g., supportive care, including immunosuppressant treatment) has been initiated.
- g. Grade 3 fatigue that resolves to ≤Grade 2 within 1 week.
- h. Grade 3 infusion reactions in the absence of an optimal pretreatment regimen, which is defined as acetaminophen or a comparable non-steroidal anti-inflammatory agent, plus an antihistamine and corticosteroids.
- i. Grade 3 or 4 infection or neutropenic fever although Grade 4 infection uncontrolled for > 7 days will be considered DLT.
- j. Grade 3 electrolyte disturbances (hyperkalemia, hypophosphatemia, hyperuricemia, etc.) that resolves to ≤Grade 2 or baseline within 1 week. Grade 4 hyponatremia not responsive to appropriate fluid management for dinutuximab will be considered a DLT.
- k. Other single laboratory values out of normal range that have no clinical correlate and resolve to Grade ≤1 or to baseline within 7 days with adequate medical management.
- 1. Tumor flare phenomenon defined as local pain, irritation, or rash localized at sites of known or suspected tumor.
- m. Grade 3 decrease in vision that resolves to grade 1 or better before the next dose dinutuximab will not be considered a DLT and dose will be modified as per Section 7.3.2. Eye disorders such as sluggish light reflex or other visual disturbances that do not cause visual loss will not be considered DLT. Subtotal or total vision loss will be considered a DLT.
- n. Capillary leak syndrome and/or hypotension (grade 3-4) which resolves to ≤Grade 2 or baseline within 8 hours with maximum supportive care.

Management and dose modifications associated with the above adverse events are outlined in Section 7.

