# 6.2 Regimen Description and Supportive Care Guidelines

- **6.2.1** Hu5F9-G4 (Magrolimab) and Dinutuximab (Unituxin®) Agent Administration
- 6.2.1.1 Dose Finding Cohort (Arm A) Regimen

Table 5: Regimen Description for Dose Finding Cohort (Arm A)

Agent	Premedications; Precautions	Dose	Route	Schedule	Cycle Length
Hu5F9-G4 (magrolimab)	Administer according to guidelines in Section 6.2.1.3. Acetaminophen oral (PO) and diphenhydramine (IV) or a comparable regimen up to 15 minutes before the first two doses of Hu5F9-G4 (magrolimab), and in case of re-priming of the patient after > 4 weeks interruption in treatment. Monitor for infusion reactions during and	mg) of acetaminophen; 0.5 - 1 mg/ kg (max 50 mg) of diphenhydramine^  Priming: Hu5F9-G4 (magrolimab) - 1 mg/kg  "Single Agent Safety Lead-In": Hu5F9-G4 (magrolimab) 30 mg/kg*  Cycles 1 and subsequent cycles: Hu5F9-G4 (magrolimab) 30	PO; Diphenhydramin e IV  Priming: Infuse IV (peripheral or central line) over 3 hours (± 30 min)  Subsequent infusions: Infuse IV over 2 hours	-	21 days (3 weeks)
Dinutuximab	Administration requires premedication	10 mg/kg (max 650 mg) of		Cycles 1 (Week 1): Days 2-5;	

(acetaminophen -	- 1 mg/ kg (max 50	e^ IV (no need to	Cycle 2 (Week
oral,	0 0 1	be repeated if	` `
diphenhydramine -	O ,	dinutuximab	-,- = -,-
IV, and analgesia)			Subsequent
and hydration prior to		follows previous	
initiation according to		drug infusion)	
Section 6.2.1.4	Dinutuximab - 17.5		week of each
	$mg/m^2$	Analgesia as	subsequent
		described below	cycle
		in Section	
		6.2.1.4 .	
		Dinutuximab in	
		100 mL bag of	
Administer 0.9%		0.9% Sodium	
Sodium Chloride		Chloride	
Injection USP 10		Injection USP	
mL/kg as an IV over 1		(mix by gentle	
hour prior to initiating		inversion - DO	
drug infusion		NOT shake)	

\* Dose will be de-escalated to 20 mg/kg if 2 or more patients develop DLT during the "Single Agent Safety Lead-In" or Cycle 1.

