#### 6.7 General Concomitant Medication

Medications, including reason for use, date(s) of administration, and dosage information, taken within 28 days prior to the start of treatment will be recorded. Concomitant medications, including medications for AEs, will continue to be recorded up to 30 days after treatment discontinuation. This includes any medication or vaccine, including over-the-counter or prescription medicines, vitamins, and/or herbal supplements. The investigator should be alerted if the patient is taking any agent known to affect the study agent(s) or with the potential for drug interactions. Following treatment discontinuation, information on subsequent anti-cancer therapies will be recorded.

Because there is a potential for interaction of Hu5F9-G4 (magrolimab) and Dinutuximab with other concomitantly administered drugs, the case report form must capture the concurrent use of all other drugs, over-the-counter medications, or alternative therapies. The Principal Investigator should be alerted if the patient is taking any agent known to affect or with the potential for drug interactions. The study team should check a frequently updated medical reference for a list of drugs to avoid or minimize use of.

For all prohibited and/or restricted concomitant medications, treatment and supportive care while receiving protocol therapy, please refer to inclusion/exclusion criteria (section 3.0).

Pharmacologic doses of systemic corticosteroids should be used ONLY for life-threatening conditions (i.e. life-threatening allergic reactions and anaphylaxis such as bronchospasm, stridor) unresponsive to other measures. The use of dexamethasone as an anti-emetic is not permitted. Corticosteroid therapy can be used as a premedication for transfusion in patients known to have a history of transfusion reactions or for treatment of an unexpected transfusion reaction (hydrocortisone 2 mg/kg or less or an equivalent dose of an alternative corticosteroid). The use of steroids during protocol therapy requires clear justification and documentation.

Patients who use oral contraceptives should continue their use. Males and females of reproductive potential should use highly effective means of contraception (refer to section 6.8).

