# **7.2.1** Management of Infusion-related Reactions (IRR)

The most common adverse events associated with IRRs include chills, pyrexia, back pain, nausea, vomiting, hypotension, dyspnea, and headache. These primarily occur with the first two doses of Hu5F9-G4 (magrolimab), and are mostly observed during the infusion or several hours afterward.

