#### **Preventive Measures**

Premedication should include oral acetaminophen and an antihistamine (IV or oral) before the first two doses of Hu5F9-G4 (magrolimab) or in case of re-priming of Hu5F9-G4 (magrolimab), please refer to Table 5.

Recommendations for the management of IRRs are provided below.

Toxicity	Severity	Management
Infusion-related Reactions	Grade 1 – mild transient reaction	Remain at bedside and monitor patient until recovery from symptoms.
	Grade 2 - infusion interruption is indicated, but patient responds promptly to symptomatic treatment (e.g.,	Stop the Hu5F9-G4 (magrolimab) infusion, begin an intravenous (IV) infusion of normal saline, and consider treating the patient with diphenhydramine (0.5 – 1 mg/kg, max 50 mg) IV (or equivalent) and/or 10 mg/kg, max dose 650 mg oral acetaminophen.  Remain at bedside and monitor patient until resolution of symptoms.
	antihistamines, non-steroidal	Corticosteroid therapy may also be given at the discretion of the Investigator.
	anti-inflammatory drugs, narcotics, corticosteroids,	If the infusion is interrupted, wait until symptoms resolve, then restart the infusion at 50% of the original infusion rate.
	IV fluids); and prophylactic medications are	If no further complications occur after 1 hour ( $\pm$ 10 minutes), the rate may be increased to 100% of the original infusion rate. Monitor the patient closely.
	indicated for ≤24 hours	If symptoms recur, stop infusion and disconnect patient from the infusion apparatus. No further Hu5F9-G4 (magrolimab) will be

Toxicity	Severity	Management
		administered at that visit.
		Premedications should be considered before any future infusions.
		The amount of Hu5F9-G4 (magrolimab) infused must be recorded on the case report form (eCRF).
		Patients who experience a grade 2 IRR during the post-infusion observation period that does not resolve during that time should be observed until the AE resolves, with vital sign measurements as medically indicated for the management of the AE.
	Grade 3 -	Immediately discontinue infusion of Hu5F9-G4 (magrolimab).

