	prolonged infusion related reactions (e.g., not rapidly responsive to symptomatic medication and/or brief interruption	Begin an IV infusion of normal saline, and consider treating the patient as follows: Administer bronchodilators, epinephrine 0.01 mg/kg up to 0.5 mg of a 1:1,000 solution for subcutaneous administration or 0.01 mg/kg of a 1:10,000 solution injected slowly for IV administration and/or diphenhydramine 0.5 – 1 mg/kg IV with methylprednisolone 1 mg/kg IV (or equivalent), as needed.
	of infusion), or recurrence of	The patient should be monitored until the Investigator is comfortable that the symptoms will not recur.
	symptoms following initial improvement, or where	Patients who have grade 4 IRRs occurring with the first dose (priming dose) will be permanently discontinued from study treatment.
	hospitalization is indicated for other clinical sequelae (e.g., renal impairment, pulmonary infiltrates)	Patients who experience grade 3 IRRs must be given premedication prior to all subsequent doses. In this setting, premedication with oral acetaminophen (10 mg/kg, max dose 650 mg), oral or IV diphenhydramine (0.5 – 1 mg/kg, max dose 50 mg), and IV dexamethasone (0.6 mg/kg), or a comparable regimen, is recommended for the subsequent 2 doses. Continued premedication with corticosteroids beyond these 2 doses may be administered at the discretion of the treating physician.
	or Grade 4 - having life-threatening	Patients who receive premedication with a corticosteroid and still experience a grade 3 or 4 infusion-related reaction will be permanently discontinued from study treatment.
	consequences and where urgent	Investigators should follow their institutional guidelines for the treatment of anaphylaxis.
	intervention indicated)	All patients with grade 3 or greater IRRs will be observed until the AE(s) resolves or stabilizes, with vital sign measurements and additional evaluations, as medically indicated for the management of the AE(s).

In the case of late-occurring hypersensitivity symptoms (e.g., appearance of localized or generalized pruritus after Day 1 but within 1 week after treatment), symptomatic treatment may be given (e.g., oral antihistamine or corticosteroids).

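### Section 6.3(h) ties the infusion-reaction DLT to corticosteroid premedication that the regimen does not include, so under protocol-specified premedication a first Grade 3 reaction is not counted

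*Combined protocol and SAP*

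**What the plan says.** Section 6.3 counts non-hematological toxicity of Grade 3 or worse as a DLT, with listed exceptions. Item h excepts "Grade 3 infusion reactions in the absence of an optimal pretreatment regimen", and it spells out what is required as an "optimal pretreatment regimen, which is defined as acetaminophen or a comparable non-steroidal anti-inflammatory agent, plus an antihistamine and corticosteroids".

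The premedication specified elsewhere is different:

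- **Magrolimab.** Table 5 gives "Acetaminophen oral (PO) and diphenhydramine (IV) or a comparable regimen up to 15 minutes before the first two doses of Hu5F9-G4 (magrolimab"; Tables 6 and 7 follow the same pattern. Section 7.2.1, Preventive Measures, says "Premedication should include oral acetaminophen and an antihistamine (IV or oral) before the first two doses of Hu5F9-G4 (magrolimab", and for re-priming. No corticosteroid is named.
- **Dinutuximab.** Section 6.2.1.4 lists an antihistamine and acetaminophen, with ibuprofen as needed. No corticosteroid is named.
- **General rule.** Section 6.7 says "Pharmacologic doses of systemic corticosteroids should be used ONLY for life-threatening conditions", with a separate allowance for transfusion premedication. Section 3.2.10 excludes patients on systemic corticosteroids at treatment start, with narrow exceptions.

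Corticosteroid premedication first appears after a reaction. In the Section 7.2.1 management table, a Grade 3 magrolimab reaction leads to a regimen including dexamethasone, which, "or a comparable regimen, is recommended for the subsequent 2 doses". In Section 7.3.2.2, hydrocortisone is added on re-challenge when a dinutuximab reaction recurs.

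**The concern.** The exception reads as if it were for patients whose premedication fell short. Under the protocol's own regimen, every patient falls short of item h's definition at first exposure. Section 7.2.1 says of magrolimab infusion reactions: "These primarily occur with the first two doses of Hu5F9-G4 (magrolimab". In the Safety Lead-In those are the priming dose and the first full dose, both inside the DLT window. Premedication is not routinely required from the third dose on, so a first Grade 3 reaction at that point is exempt as well.

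Safety and the recommended phase 2 dose are primary objectives (Section 1.1), and one or two DLTs settle each dose decision (Section 6.1.1). The Clinical Safety Summary in Section 2.1.6 makes infusion reaction the most frequent serious reaction attributed to magrolimab. If first Grade 3 reactions drop out of the count, a dose can be cleared whatever their rate.

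**Working it through.** **Textual check.**

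1. Item h requires three components: antipyretic, antihistamine, corticosteroid.
2. The routine regimens for both antibodies supply the first two only.
3. A patient treated as specified therefore lacks the defined regimen at a first reaction.
4. A first Grade 3 infusion reaction then meets the exception and is not a DLT. A repeat Grade 3 reaction after steroid premedication would count, and item h does not cover Grade 4.

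**Background rates (Section 2.1.6).** Any-grade related infusion reaction is 25.7% of 401 patients. Related serious infusion reactions are 21 of 86 related serious events: 21/86 = 24.4%, and 21/401 = 5.2 events per 100 patients. These count serious events, not patients with Grade 3 reactions. The documents give no Grade 3 rate for this combination.

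**Effect on one window.** The plan states no operating characteristics for the dose-finding rule, so there is no figure of its own to reproduce. Under Section 6.1.1 a dose clears with 0 DLTs in 3 patients, or with 1 in the first 3 and 0 in the next 3. With per-patient DLT probability p and q = 1 − p:

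P(clear) = q³ + 3pq² × q³ = q³ + 3pq⁵

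Let d be the rate of other DLTs and r the Grade 3 infusion-reaction rate, both assumed and taken as independent. With the exemption p = d. If all such reactions counted, p = 1 − (1 − d)(1 − r).

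For d = 15%:

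- Exempt: p = 0.15, so 0.85³ + 3(0.15)(0.85⁵) = 0.614 + 0.200 = 0.814.
- r = 5%: p = 1 − 0.85 × 0.95 = 0.1925, P(clear) = 0.725.
- r = 10%: p = 1 − 0.85 × 0.90 = 0.235, P(clear) = 0.632.
- r = 20%: p = 1 − 0.85 × 0.80 = 0.32, P(clear) = 0.454.

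Probability of clearing one window, over a range of d:

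| Other DLTs (assumed) | Exempt, any r | Counted, r = 5% | r = 10% | r = 20% |
|---|---|---|---|---|
| 5% | 97.3% | 91.0% | 82.4% | 62.2% |
| 10% | 90.6% | 82.4% | 73.0% | 53.6% |
| 15% | 81.4% | 72.5% | 63.2% | 45.4% |

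Under the exemption the result does not change with r.

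**Where it bears on the dose level.** Priming is 1 mg/kg for everyone (Section 6.1), and dinutuximab is 17.5 mg/m² at both levels (Table 4). De-escalation changes only the magrolimab doses after priming. Reactions to priming or to dinutuximab therefore say little about 30 against 20 mg/kg; the full magrolimab doses from week 2 are where the exemption matters for that choice. The table counts all Grade 3 reactions alike, so it overstates the dose-relevant part.

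**The case against.** The strongest reply is that item h is deliberate. Section 7.2.1 keeps a patient on treatment, with added premedication, after a first Grade 3 magrolimab reaction, and stops treatment if Grade 3 or 4 recurs despite a corticosteroid. Item h draws the DLT line in the same place. Section 6.1.1.1 also removes any patient with a Lead-In DLT, so counting first reactions would contradict the continuation rule. This is a tenable reading, and it means a one-sided rewrite of item h would create a new conflict. But item h does not state that intent. It describes missing steroids as a departure from optimal care, when on this protocol that is the routine. Sections 6.7 and 7.2.1 still pull apart on steroid premedication, although 6.7 does contemplate justified and documented steroid use.

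A reader might infer that a first Grade 3 reaction can never count, or that the trial cannot see this toxicity. The documents do not support either:

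- Tables 5 to 7 allow a comparable premedication regimen, which a site might build with a steroid. After a Grade 2 reaction, Section 7.2.1 suggests premedication without naming agents.
- Sections 3.2.10 and 6.7 permit hydrocortisone as transfusion premedication, which could fall close to dosing.
- An event graded as anaphylaxis has no exception in Section 6.3.
- Grade 3 infusion reactions exceed the Grade 2 threshold in the magrolimab list of expedited-reporting exceptions (Section 10.1.1.1), and safety data are reviewed in real time, weekly and by the monitoring committee (Sections 6.4, 13.1). These reviews do not enter the DLT count, but they keep the events visible.

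In Arm B, reaching the DLT threshold in Section 6.4 prompts a discussion about re-assessing the dose, not automatic de-escalation.

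**Conclusion.** The point holds for patients premedicated as the protocol specifies: a first Grade 3 infusion reaction to either antibody is excepted, and the dose-finding rule does not respond to its rate. It does not hold as an absolute, for the reasons above.

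The size is uncertain. Near a 5% Grade 3 rate the effect is modest: 81% against 73% clearance with other DLTs at 15%, or 97% against 91% with other DLTs at 5%. It becomes large only if the rate in this population is well above that. All these figures rest on assumed rates, independence, and every Grade 3 reaction counting once the exemption is lifted. Items f and n would exempt some transient components if they were graded separately, which would shrink the difference. Whatever the size, the definition behind a primary objective uses a condition that the specified regimen does not meet, and that needs resolving in the text.

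**What to change.** Reconcile Section 6.3(h) with:

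- the premedication in Tables 5 to 7, Section 6.2.1.4 and Section 7.2.1;
- the corticosteroid restriction in Section 6.7;
- the management after a Grade 3 reaction in Section 7.2.1;
- the removal rule after a Lead-In DLT in Sections 6.1.1.1 and 6.5.1.

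The amended item h should do one of two things: refer to premedication that patients receive under the protocol, or state openly that first Grade 3 infusion reactions are exempt. Which of these applies, and whether corticosteroids belong in the regimen, is for the sponsor to decide.

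Then list any Grade 3 infusion reactions already recorded in the DLT windows, with the dose at which each occurred and the premedication given. Re-read them against the reconciled text and report them beside the DLT count.

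The cost is a short amendment and a review of existing adverse-event records. Depending on the sponsor's decision, de-escalation may become more likely.

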### **6.4** Dose Expansion Cohorts

Upon determining RP2D, enrollment to 4 expansion cohorts will proceed to evaluate evidence of clinical activity (cohorts B1-3) and safety/feasibility of using this combination drug approach after surgery (cohort B4) (Figure 2).

Cohort B1 – Confirmed neuroblastoma: measurable neuroblastoma/ganglioneuroblastoma

Cohort B2 – Evaluable neuroblastoma

Cohort B3 – Measurable osteosarcoma

Cohort B4 – Resectable, pulmonary only relapsed osteosarcoma

All subjects will receive the priming dose of 1 mg/kg Hu5F9-G4 (magrolimab) on Day 1 of week 1. On Day 1 of week 2, subjects will receive Hu5F9-G4 (magrolimab) at RP2D followed by 17.5 mg/m² dinutuximab IV on Days 2-5. Then, they will receive Hu5F9-G4 (magrolimab) at RP2D on Day 1 of week 3 and week 4 (**Figure 2** and **Section 6.2.1.2**).

Cycle 2 will consist of Hu5F9-G4 (magrolimab) at RP2D on Day 1 of week 1 in combination with 17.5 mg/m² dinutuximab IV given on Days 2-5, followed by Hu5F9-G4 (magrolimab) at RP2D on Day 1 of weeks 2-3 (see **Figure 2** and **Section 6.2.1.2**). A disease evaluation will be conducted after Cycle 2 and Cycle 4, and then after every 4 cycles (every 12 weeks) until progressive disease or a maximum of 12 cycles (except cohort four which will have a maximum of five cycles after the patient is rendered No Evidence of Disease (NED)). After Cycle 2, each subsequent cycle will consist of Hu5F9-G4

(magrolimab) administered on Day 1 of weeks 1 and 3 of the cycle (week 2 will be a week of rest), with dinutuximab administration on Day 2-5 of week 1.

Doses of Hu5F9-G4 (magrolimab) and dinutuximab in the expansion cohorts may be interrupted, delayed or discontinued depending on how well the participant tolerates the treatment. Dosing visits are not skipped, only delayed. Both Hu5F9-G4 (magrolimab) and dinutuximab must be delayed at the same time. Protocol therapy must be discontinued for dose delays greater than 14 days except for reasons outlined in **Section 6.6**. In such cases, the Protocol Principal Investigator must be consulted prior to resuming treatment.

For the expansion cohorts, patients will continue to be monitored for occurrence of DLT during Cycle 1. If 2 of the first 5 patients or if  $\geq$ 2 of 6 patients experience DLT, the Principal Investigator will discuss with all study investigators and with CTEP whether further addition of patients is needed to re-assess the RP2D.

Monitoring of all safety and toxicity data is done by the Principal Investigator and the Corresponding Organization on a real-time basis as data are entered into Medidata Rave using the Web Reporting Module. All participating sites are expected to notify the Principal Investigator when a DLT has occurred.

